### **5.1. Data handling rules**

Units as provided in the SAP will be used in the analyses if these are deviated from the units provided in the Study Data Tabulation Model (SDTM) data. The viral activity parameters (i.e. virology and serology parameters) will be analyzed using log10 transformation rounded to 2 decimal places.

Historical as actual data for viral activity parameters will be used in the analysis. In the case a diluted and a non-diluted sample are present for a parameter at any time point, only the diluted sample will be included in the analysis. Historical viral activity measurements will not be imputed. The actual measurements will be imputed as follows:

- **HBsAg** values were tested with an upper limit of quantification of 124925.00 IU/mL and a lower limit of quantification of 0.05 IU/mL. Samples for the determination of HBsAg were processed in real-time using an assay such as the ARCHITECT platform (Abbott Laboratories).
  - Values above the upper limit of quantification (124925.00 IU/mL), will be imputed by the value of round (ULOQ+(ULOQ/10)) IU/mL in the analysis.
  - Values below the lower limit of quantification (0.05 IU/mL) will be imputed by a rounded value of (LLOQ/2) IU/mL in the analysis.
  
- **HBeAg** values were tested with an upper limit of quantification of 1400.00 IU/mL and a lower limit of quantification of 0.11 IU/mL.
  - Values above the upper limit of quantification (1400.00 IU/mL), will be imputed by a value of round (ULOQ+(ULOQ/10)) IU/mL in the analysis.
  - Values below the lower limit of quantification (0.11 IU/mL) will be imputed by a rounded value of (LLOQ/2) IU/mL in the analysis.

---

- **HBcrAg** values were tested within a measurement range of 3.0 LogU/mL - 9.0 LogU/mL
  - Values below lower limit of quantification (<3.0 LogU/mL) will be imputed by 2.7 log U/mL
  - Values above the upper limit of quantification (official ULOQ = 7 Log U/ml but with dilution ULOQ= 9.0 Log U/ml) will be imputed by value of round (ULOQ+(ULOQ/10)) log10U/mL with or without dilution method
- **Plasma HBV DNA** values were measured by the HBV COBAS AmpliPrep – COBAS TaqMan, V. 2.0 test (lower limit of quantification 20 IU/mL). Values below the lower limit of quantification (20 IU/mL) will be imputed as follows:
  - Values below the lower limit of quantification (20 IU/mL), but target detected will be imputed by a value of 15 IU/mL in the analysis.

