HbcrAg Response	Subject who has achieved a HBV DNA level <2 log10 IU/mL per time point	These proportions will also be included per analysis phase and analysis period. A subject will be included in the numerator if the response category is at least once met within the analysis phase/period.
	Subject who has achieved a HBV DNA level <3 log10 IU/mL per time point	
	Subject who has achieved a HBV DNA level $\geq 2 - < 3$ log10 IU/mL per time point	
HbsAg Reduction	Subject who has HbsAg reduced by > 0.3 log10 IU/mL from baseline per time point	These proportions will also be included per analysis phase and analysis period. A subject will be included in the numerator if the response category is at least once met within the analysis phase/period.
	Subject who has HbsAg reduced by > 0.5 log10 IU/mL from baseline per time point	
	Subject who has HbsAg reduced by > 1 log10 IU/mL from baseline per time point	
	Subject who has HbsAg reduced by > 2 log10 IU/mL from baseline per time point	
	Subject who has HbsAg reduced by > 3 log10 IU/mL from baseline per time point	
HbeAg Reduction	Subject who has HbeAg reduced by > 0.5 log10 IU/mL from baseline per time point	These proportions will also be included per analysis phase and analysis period. A subject will be included in the numerator if the response category is at least once met within the analysis phase/period.
	Subject who has HbeAg reduced by > 1 log10 IU/mL from baseline per time point	
	Subject who has HbeAg reduced by > 2 log10 IU/mL from baseline per time point	
HBV DNA Reduction	Subject who has HBV DNA reduced by > 1 log10 IU/mL from baseline per time point	These proportions will also be included per analysis phase and analysis period.

	Subject who has HBV DNA reduced by $> 2 \log_{10}$ IU/mL from baseline per time point	A subject will be included in the numerator if the response category is at least once met within the analysis phase/period.
	Subject who has HBV DNA reduced by $> 3 \log_{10}$ IU/mL from baseline per time point	
	Subject who has HBV DNA reduced by $> 1 \log_{10}$ IU/mL from baseline at week 4 and confirmation at week 8.	
HBV RNA Reduction	Subject who has HBV RNA reduced by $> 1 \log_{10}$ cp/mL from baseline per time point	These proportions will also be included per analysis phase and analysis period. A subject will be included in the numerator if the response category is at least once met within the analysis phase/period.

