	Subject who has HBV RNA reduced by $> 2 \log_{10}$ cp/mL from baseline per time point	
	Subject who has HBV RNA reduced by $> 3 \log_{10}$ cp/mL from baseline per time point	
HbcrAg Reduction	Subject who has HBV DNA reduced by $> 0.5 \log_{10}$ IU/mL from baseline	These proportions will also be included per analysis phase and analysis period. A subject will be included in the numerator if the response category is at least once met within the analysis phase/period.

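### SAP Table 4 defines all four HBcrAg response and reduction categories in terms of HBV DNA, and renaming the marker still leaves the 2-log boundary unusable.

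*SAP*

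**What the plan says.** SAP Table 4 sets the response categories for the viral activity parameters. Its HBcrAg Response block has three criteria. The first is worded "Subject who has achieved a HBV DNA level <2 log10 IU/mL per time point". The second has the same form with the limit moved up to 3 log10, and the third takes the band from 2 to below 3 log10; both again name HBV DNA and give the unit as IU/mL.

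The HBcrAg Reduction block has a single criterion: "Subject who has HBV DNA reduced by $> 0.5 \log_{10}$ IU/mL from baseline".

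The Secondary Analysis part of SAP Section 5.3 commits to tabulating these categories for each parameter, by time point and by period.

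SAP Section 5.1 sets the scale on which HBcrAg is analysed. The assay range runs from 3.0 to 9.0 log U/mL, and any result under the lower limit "will be imputed by 2.7 log U/mL". The introduction to SAP Section 5 applies these handling rules to the primary, secondary and exploratory analyses.

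The unit is not consistent. SAP Section 4.2.2 gives baseline HBcrAg in log10 IU/mL, as do the Table 4 rows, while Section 5.1 uses log U/mL.

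**The concern.** There are two faults, one behind the other.

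The first is the marker. A program that follows Table 4 to the letter would print HBV DNA results under an HBcrAg heading, and they would look plausible. Protocol Section 4.1 requires virologically suppressed subjects to have HBV DNA below 60 IU/mL at screening. Nearly all of them would therefore meet a limit of 100 IU/mL from the start, on placebo or on active drug. Untreated subjects enter with at least 2,000 IU/mL, and Protocol Section 1.1 reports Phase 1 mean HBV DNA declines of 2.16 to 2.89 log10 at Day 29. Most of those on active treatment would be expected to pass a reduction limit of 0.5 log10. Neither result would contain any information on HBcrAg.

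The second is the cut-offs. Someone who spots the slip and changes only the name would still produce one row that can never be filled and two rows that are always equal. A reader could take the empty row as a finding about the drug when it follows from the assay limit and the imputation rule.

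Table 5 has no HBcrAg time-to-event rows, so Table 4 is the only place where HBcrAg categories are defined.

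**Working it through.** **Inputs.** From SAP Section 5.1: HBcrAg quantification limit 3.0 log U/mL; measured range up to 9.0 log U/mL; imputed value below the limit 2.7 log U/mL. From SAP Table 4: response cut-offs at 2 and 3 log10, and a reduction cut-off of 0.5 log10.

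**Step 1: reproduce the imputed value.** Half the quantification limit on the log scale is log10(10^3.0 / 2) = log10(500) = 2.699, which rounds to 2.7. This agrees with the SAP.

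**Step 2: which HBcrAg values can occur.** At the lower end only 2.7 (imputed) and then 3.0 upward (measured). Nothing lies below 2.7, or between 2.7 and 3.0. The upper end does not matter here.

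**Step 3: apply each criterion, first literally and then with only the marker renamed.** On the HBV DNA scale, 10^2 = 100 IU/mL and 10^3 = 1,000 IU/mL.

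| Table 4 row | As written | Marker renamed to HBcrAg, cut-off kept |
|---|---|---|
| Response, below 2 | HBV DNA <100 IU/mL; repeats a row of the HBV DNA block | Met by no possible value: always 0% |
| Response, below 3 | HBV DNA <1,000 IU/mL; repeats a row of the HBV DNA block | Met by 2.7 only: HBcrAg below the quantification limit |
| Response, 2 to below 3 | HBV DNA 100 to <1,000 IU/mL | Met by 2.7 only: same subjects as the row above |
| Reduction, more than 0.5 | HBV DNA fall >0.5 log10 | Can be met; see step 4 |

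**Step 4: the reduction row after renaming.** The lowest value a subject can reach is 2.7, so a fall of more than 0.5 requires a baseline above 2.7 + 0.5 = 3.2 log U/mL. If results are reported to one decimal, which is an assumption, the smallest such baseline is 3.3. From a baseline of 9.0 the largest measurable fall is 9.0 − 2.7 = 6.3. The cut-off is well inside the assay's range.

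**Count.** As written, 4 of 4 rows use the wrong marker. After renaming, 1 of the 3 response rows is always empty and the other 2 are identical. That leaves one usable response category and one usable reduction category.

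**The case against.** The strongest reply is that this is a visible copying slip. The block labels say HBcrAg, and HBV DNA has its own response and reduction blocks in the same table. A programmer would probably query the text rather than tabulate HBV DNA. The intended marker is indeed clear. That does not settle which cut-offs were intended, because renaming the rows leaves the 2-log boundary in place.

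The second reply concerns weight, and it stands. Protocol Section 2.1 makes HBcrAg an exploratory objective with change from baseline as its endpoint, and Protocol Section 11.3.3 has it analysed descriptively. SAP Section 5.5 also lists it as exploratory. The Time and Events schedules allow samples to be batched and only some to be tested. Maximum decrease, change from baseline and the mean and individual plots do not use these rows. HBcrAg is also absent from the SAP's list of proportions for which differences and confidence intervals may be calculated.

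A reader might infer that the assay cannot resolve any of the HBcrAg cut-offs, so that no HBcrAg response could be reported at all. The documents do not support that. The below-3 cut-off sits exactly at the quantification limit, and the 0.5-log reduction is measurable for any baseline above 3.2 log U/mL. Both would be reported once the marker is corrected.

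Nor do all four rows repeat existing HBV DNA output. Only the below-2 and below-3 rows do; the other two have no HBV DNA counterpart in Table 4.

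**Conclusion.** Table 4 is wrong as written: it defines no HBcrAg response or reduction category, because all four criteria name HBV DNA. With the name corrected, two of the three response rows still carry no information of their own: the below-2 row can never be met, and the 2-to-below-3 row duplicates the below-3 row.

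This rests on the Section 5.1 imputation being applied before the categories are derived, as the introduction to Section 5 indicates. Using the unimputed results would not help, because a value reported only as below 3.0 cannot be placed above or below 2.

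The consequence is limited to descriptive categorical displays of HBcrAg. It would go too far to treat this as a fault in a confirmatory secondary endpoint. SAP Section 5.3 does list HBcrAg as secondary, but the protocol treats it as exploratory and no formal hypothesis testing is planned. The correction is still worth making, because the SAP commits to these tables and the error would put one marker's results under another's name.

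**What to change.** In SAP Table 4:

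- Replace HBV DNA with HBcrAg in all four rows.
- Use log U/mL in these rows and in Section 4.2.2, to match Section 5.1.
- Keep the response category below 3.0 log U/mL, labelled as below the quantification limit, and the reduction of more than 0.5 log U/mL.
- Drop the below-2 and 2-to-below-3 rows. If a further response category is wanted, replace them with a cut-off above 3.0 log U/mL, chosen before HBcrAg data are reviewed by treatment. Nothing in the documents requires an extra category, so this is optional.

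The cost is an edit to four table rows and one unit, with the matching change to the programming specifications. No data collection changes.

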## SUBJECT POPULATION

### Key Inclusion Criteria

- Subjects must be 18 to 70 years of age, inclusive.
- Subjects must have CHB infection documented by:
  - Serum HBsAg-positive at screening and serum HBsAg- or HBV DNA-positive at least 6 months prior to screening;
  - Serum immunoglobulin M (IgM) anti-HBc antibody negative at screening.
- In subjects currently not being treated (Treatment Arms 1-2-3 and 6-7-8):
  - Subjects must not be receiving any CHB treatment at screening, ie,
    - Have never received treatment with HBV antiviral medicines, including NAs or interferon (IFN) products, OR
    - Have not been on treatment with HBV antiviral medicines, including NAs or IFN products, within 6 months prior to baseline (first intake of study drugs), AND
  - Subjects must be HBeAg-positive and have HBV DNA  $\geq 20,000$  IU/mL, OR be HBeAg-negative and have HBV DNA  $\geq 2,000$  IU /mL at screening, AND
  - Subjects must have HBsAg  $> 250$  IU/mL at screening, AND
  - Subjects must have ALT  $>$  upper limit of normal (ULN) and  $\leq 5 \times$  ULN at screening, determined in the central laboratory.

**Note:** If subjects were treated with investigational anti-HBV agents more than 6 months before screening, the sponsor should be contacted to discuss the case. Subjects who have received treatment with a CAM for more than 4 weeks any time prior to screening are excluded.

- In virologically suppressed subjects (Treatment Arms 4-5 and 9-10):
  - Subjects must be virologically suppressed by current NA treatment (ETV or TDF) as defined by HBV DNA <60 IU/mL at screening and at least 6 months prior to screening, AND
  - Subjects must be on the same NA treatment (ETV or TDF) and the same dose for  $\geq 12$  months prior to screening, AND
  - Subjects must have HBsAg >250 IU/mL at screening, AND
  - Subjects must have ALT  $\leq 2$ x ULN at screening.

**Note:** If subjects were treated with investigational anti-HBV agents more than 6 months before screening, the sponsor should be contacted to discuss the case. Subjects who have received treatment with a CAM for more than 4 weeks any time prior to screening are excluded.

**Note:** The current NA treatment can either be a branded product or a locally approved generic alternative (including different salt forms [eg, tenofovir maleate or succinate]). During the study, subjects will receive branded ETV (Baraclude®) or TDF (Viread®) treatment, as applicable.

- Subjects must have:

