  - Values below the lower limit of quantification (20 IU/mL, target not detected) will be imputed by a value of 5 IU/mL in the analysis.
  - Values above the upper limit of quantification (>170000000 IU/mL), will be imputed by the value of round (ULOQ+(ULOQ/10)) IU/mL in the analysis
- **HBV RNA** values were tested with an upper limit of quantification (ULOQ) and a lower limit of quantification (LLOQ), all values, even below LLOQ (4.0 log10 cp/mL) or LOD (2.49 log10 cp/mL) will be reported and all numeric values will be used in the analysis.
  - Negative or Not Detected (“TND”) values will be imputed by a value of 5 copies/mL ( $\log_{10}(5) = 0.69897$  log10 cp/mL) in the analysis.
  - Values above the upper limit of quantification (>ULOQ), will be imputed by the value of round (ULOQ+(ULOQ/10))  $\log_{10}$  cp/mL in the analysis
- **Anti-HBs** values were tested with an upper limit of quantification (ULOQ) and lower limit of quantification (LLOQ), all values, even below LLOQ (< 5.0 mIU/mL) will be reported and all numeric values will be used in the analysis.

---

- Values below LLOQ (<5mIU/mL) will be imputed by value of round (LLOQ/2) mIU/mL
- Values “>10000.00 mIU/mL” (with annotation “diluted for quantitation”) will be imputed by value of round (ULOQ+(ULOQ/10)) mIU/mL

Additionally, all other viral activity data with values below a LLOQ and not included in the imputation rules above will be imputed by the absolute value divided by 2 and rounded to the amount of decimal place provided in the dataset.

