	Time to HBV DNA < LLQ for target not detected	Subjects who did not achieve HBV DNA<LLQ for target not detected will be censored at the last HBV DNA assessment
	Time to HBV DNA < LLQ for target detected	Subjects who did not achieve HBV DNA<LLQ for target detected will be censored at the last HBV DNA assessment
HBV DNA Reduction	Time to a HBV DNA reduction of > 1 log10 IU/mL from baseline	Subjects who did not reduce “HBV DNA by >x log 10 IU/mL” from baseline will be censored at the last HBV DNA assessment
	Time to a HBV DNA reduction of > 2 log10 IU/mL from baseline	
	Time to a HBV DNA reduction of > 3 log10 IU/mL from baseline	
HBV RNA Response	Time to a HBV RNA level <100 cp/mL	Subjects who did not achieve “HBV RNA<xxxx cp/mL” will be censored at the last HBV RNA assessment
	Time to a HBV RNA level <1000 cp/mL	
	Time to a HBV RNA level <2000 cp/mL	
	Time to a HBV RNA level <20000 cp/mL	
	Time to HBV RNA target not detected	Subjects who did not achieve HBV RNA target not detected will be censored at the last HBV RNA assessment
	Time to HBV RNA < LLOQ	Subjects who did not achieve HBV RNA <LLOQ will be censored at the last HBV RNA assessment
	Time to a HBV RNA level <250 cp/mL	Subjects who did not achieve HBV RNA <250IU/ml will be censored at the last HBV RNA assessment
HBV RNA Reduction	Time to a HBV RNA reduction of > 1 log10 cp/mL from baseline	Subjects who did not reduce HBV RNA by “>xx log 10 cp/mL” from baseline will be censored at the last HBV RNA assessment
	Time to a HBV RNA reduction of > 2 log10 cp/mL from baseline	
	Time to a HBV RNA reduction of > 3 log10 cp/mL from baseline	

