### 5.2.1 Secondary Analysis

- Descriptive statistics of the actual values (original unit and log10 transformed values) and the change from baseline (log10 transformed values) over time for qualitative viral activity parameters according to the specification described in section 2.6 will be included.
- LS means (SE) of change from baseline (and 95% confidence interval) for qualitative viral activity parameters per time point and overall based on log10 transformed values will be analyzed by subject population and part using mixed effects model for repeated measures similar as described in section 5.2.1.1.. Also P-values for treatment, time, their interaction and overall will be added.
- LS means (SE) of change from baseline (and 95% confidence interval) for qualitative viral activity parameters (except for HBeAg) per time point and overall based on log10

---

transformed values will be analyzed by subject population, part and by HBeAg status using mixed effects model for repeated measures similar as described in section 5.2.1.1. Also P-values for treatment, time, their interaction and overall will be added.

- A tabulation of the proportion of subjects with virological breakthrough during 24 week treatment and during 48 week treatment (only subjects with treatment extension) will be included.
- A tabulation of the proportion of subjects with viral relapse will be provided. For the purpose of the analysis, the denominator will only include those subjects with values Yes and No.
- Descriptive statistics of the maximum decrease from baseline ( $\log_{10}$  transformed values) over time for qualitative viral activity parameters according to the specification described in section 2.6 will be included.
- A tabulation of the status change from baseline at week 24 and at week 48 (only subjects with treatment extension) will be displayed by viral activity parameter.
- A tabulation of the proportion of subjects who meet the criteria of response categories per time point defined in section 5.3.1 will be displayed by viral activity parameter.
- A tabulation of the proportion of subjects who meet the criteria of response categories per period defined in section 5.3.1 (additional information in the table) will be displayed by viral activity parameter.
- A tabulation of the qualitative result of HBeAg and HBsAg per timepoint (week 24 and week 48) will be included.
- A tabulation of the biochemical response per time point will be included.

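### HBV DNA log10-reduction categories and time to reduction include virologically suppressed subjects, who have almost no room to fall, so all-population comparisons with monotherapy reflect arm composition

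*SAP*

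**What the plan says.** The protocol's key inclusion criteria admit suppressed subjects (Arms 4, 5, 9 and 10) "as defined by HBV DNA <60 IU/mL at screening and at least 6 months prior to screening". SAP 5.1 gives an HBV DNA assay LLOQ of 20 IU/mL. Results below it "but target detected will be imputed by a value of 15 IU/mL in the analysis", or, if "target not detected) will be imputed by a value of 5 IU/mL in the analysis". Virology parameters "will be analyzed using log10 transformation rounded to 2 decimal places".

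SAP Table 4 defines HBV DNA reductions of more than 1, 2 and 3 log10 per time point and per period, the first worded "Subject who has HBV DNA reduced by > 1 log10 IU/mL from baseline per time point", plus a row for >1 log10 at Week 4 confirmed at Week 8. Table 5 adds, for example, "Time to a HBV DNA reduction of > 1 log10 IU/mL from baseline", calculated for each subject, with non-achievers censored at their last HBV DNA assessment. None of these entries names a subject population.

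SAP 2.6 asks for tables by subject population, including an all-population version, unless otherwise specified. Its main column layout puts pooled placebo+NA, each monotherapy group and each combination group side by side. Protocol 11.3 plans monotherapy versus placebo+NA, combination versus placebo+NA and monotherapy versus combination, both overall and by population. It extends these comparisons to further virological markers.

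For change from baseline, SAP 5.3 (Secondary Analysis) says that LS means "will be analyzed by subject population and part using mixed effects model for repeated measures similar as described in section 5.2.1.1".

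**The concern.** A log10-reduction category is informative only if the subject can reach it. Subjects whose virus is already suppressed by their NA have little or no measurable range left, so their non-response in these rows carries no information about the drug.

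Suppressed subjects are 80 of the 220 planned (40 of 110 per part), and they are unevenly spread over the regimens. Monotherapy is given only to untreated subjects. JNJ-56136379+NA and placebo+NA are given in both populations. An all-population table therefore compares a fully untreated column with columns that are half suppressed. A reader could take a difference created by that mix for a difference between regimens.

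Elsewhere the SAP limits endpoints to subjects who can show them. ALT normalization requires raised ALT at baseline, viral relapse requires HBV DNA below 20 IU/mL at end of treatment, and HBeAg seroclearance is for HBeAg-positive subjects. The Week 4/8 treatment-failure rule on HBV DNA decline applies to treatment-naïve subjects only. The reduction categories have no such limit, and neither does Table 4's own Week 4/8 row.

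**Working it through.** The documents give no expected rate or power for the HBV DNA reduction endpoints, so there is no planned figure to reproduce. The check is direct arithmetic.

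**Inputs.** Entry limit below 60 IU/mL (protocol inclusion criteria). LLOQ 20, imputed values 15 and 5, logs rounded to 2 decimals (SAP 5.1). Planned arm sizes per part: untreated 30 monotherapy, 10 placebo+NA, 30 JNJ-56136379+NA; suppressed 10 placebo+NA, 30 JNJ-56136379+NA (protocol 3.1).

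**Attainable fall = log10(baseline) − log10(post-baseline), suppressed subject within the entry limit**
- Quantifiable range: 59 to 20 IU/mL = 1.77 − 1.30 = 0.47.
- To detected below LLOQ: 59 to 15 = 1.77 − 1.18 = 0.59.
- To not detected: 59 to 5 = 1.77 − 0.70 = 1.07 (limit at 60: 1.78 − 0.70 = 1.08).
- From an imputed baseline of 15 to 5: 1.18 − 0.70 = 0.48.

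**Which categories can be met**
- >1 log10 to not detected needs a baseline above 5 × 10 = 50. With rounded logs, 50 gives 1.70 − 0.70 = 1.00 (not met) and 51 gives 1.71 − 0.70 = 1.01 (met). So only baselines of 51-59 qualify, and only through the imputed 5.
- >2 log10 needs a baseline above 5 × 100 = 500 IU/mL.
- >3 log10 needs a baseline above 5 × 1,000 = 5,000 IU/mL. Neither of the last two is possible within the entry limit.

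**Untreated subjects for comparison.** The entry minimum is 2,000 IU/mL (HBeAg-negative) or 20,000 (HBeAg-positive). Falls from these minima to 20 are 2.00 and 3.00 log10. To 5 they are 2.60 and 3.60. An HBeAg-negative subject entering near 2,000 also cannot pass 3 log10, but such subjects are randomised across all the untreated arms.

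**Ceilings for >2 and >3 log10 set by population mix (all-population columns, planned numbers)**

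| Column | Untreated | Suppressed | Ceiling |
|---|---|---|---|
| Monotherapy, per dose | 30 | 0 | not lowered |
| JNJ-56136379+NA, per dose | 30 | 30 | 30/60 = 50% |
| Placebo+NA, pooled | 20 | 20 | 20/40 = 50% |
| All JNJ-56136379, per dose | 60 | 30 | 60/90 = 67% |

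Suppose 80% of untreated subjects pass 2 log10 under both active regimens. The all-population table then shows 80% for monotherapy and 0.80 × 30/60 = 40% for JNJ-56136379+NA, with no difference between the regimens in the subjects who can respond. For JNJ-56136379+NA versus placebo+NA the mix is the same on both sides, so the untreated difference is halved rather than reversed.

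**Mean change in suppressed subjects.** Each switch from detected to not detected scores a fixed 0.48 log10, about the whole quantifiable range of 0.47. The documents do not give the share who switch. Assuming that all start at 15, shares of 10%, 25% and 50% give mean changes of −0.05, −0.12 and −0.24 log10.

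**The case against.** The strongest reply is that the damage is contained. The study is exploratory, the primary endpoint is HBsAg, untreated results are tabulated separately, and no decision rule uses the >2 or >3 log10 rows. Empty rows under the label virologically suppressed explain themselves. All of this stands. It does not cover the all-population table, where the mix is hidden inside the percentages.

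A second reply concerns reach. For the proportions, SAP 5.3 defines overall as pooling HBeAg status, not populations. For Table 5, the Secondary Analysis list names no time-to-event analysis. Both observations are correct. The all-population reading rests on SAP 2.6 and protocol 11.3, which apply unless something else is specified, and nothing else is.

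Several stronger inferences are tempting, and the documents do not support them:
- **That the HBV DNA MMRM mixes the two populations.** It is run by population and part. The pooled version only adds HBeAg status as a fixed effect.
- **That log10 change in suppressed subjects is purely an artefact.** Detected versus not detected is a real assay result, values of 20-59 IU/mL and all rises are measured, and the same constants apply to every arm. How far the constants dominate depends on the share below LLOQ, which is not given.
- **That larger falls can never occur.** The limit of 60 applies at screening, whereas baseline is the last pre-dose value (SAP 2.2). A Day 1 value above 60 is possible, though a fall from it would largely be regression from a blip.
- **That interpretable output is missing.** Table 4 already has below-LLOQ detected and not-detected categories.
- **That change from baseline should be dropped in this population.** Protocol 2.1 makes it a secondary endpoint evaluated by population, and protocol 11.3.3 specifies the LS-mean model for HBV DNA.

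**Conclusion.** The concern holds for the reduction categories and for time to reduction. From a baseline within the entry limit, suppressed subjects can fall at most 1.07 log10. They cannot meet >2 or >3 log10, and they can meet >1 log10 only from 51-59 IU/mL through the imputed 5. In all-population output the >2 and >3 log10 proportions are capped near 50% for JNJ-56136379+NA and placebo+NA, while the monotherapy columns have no such cap. Comparisons with monotherapy there partly reflect who was enrolled in each arm.

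This rests on the planned arm sizes, on baselines within the entry limit, and on SAP 2.6 applying to these tables as written. The subgroup-omission clause in SAP 5.2.1.1 covers too little data, not a floor, so it does not resolve the problem. The primary HBsAg analysis, the untreated-population HBV DNA results and the by-population MMRM in untreated subjects are unaffected.

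**What to change.** 1. In SAP Tables 4 and 5, limit the denominator of the HBV DNA reduction categories (>1, >2 and >3 log10, and the Week 4/8 row) and of time to reduction to subjects currently not being treated. Apply this to the all-population rows as well, and state the reason.
2. For suppressed subjects, keep the protocol-specified change from baseline as descriptive output. Add a note that values below LLOQ are imputed and that one detected-to-not-detected switch equals 0.48 log10.
3. Base interpretation in suppressed subjects on the existing Table 4 categories for below LLOQ detected and not detected, and add a shift table from baseline.

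The cost is SAP wording, a footnote and a few table shells. No new data are needed. Protocol 2.1 leaves the HBV DNA response subcategories to the SAP, so item 1 can be made there, and item 2 keeps the by-population secondary endpoint intact.
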